2.5. Exploratory Endpoints

- Percentage of patients with dose-adjusted (to 100 U/kg) ASNase activity >100 U/L at 14 days following the *first* and *fourth* infusions (nadir);
- Percentage of patients with ASNase activity >400 U/L at 14 days following the *first* and *fourth* infusions (nadir);
- Clinical endpoints: complete remission rate, relapse rate, relapse-free survival (RFS), event-free survival (EFS).

Sponsor:	NOPHO – Nordic Society of Pediatric Hematology & Oncology		
Protocol:	NOR-GRASPALL 2016		
Document Version No.:	2.0	Document Date:	14-May-2021

3. STUDY DESIGN

3.1. Synopsis of Study Design

This is a single arm, multicenter, multinational study to assess the pharmacological activity, safety and immunogenicity of eryaspase in combination with the NOPHO ALL 2008 or ALLTogether pilot protocol chemotherapy administered as second line treatment to children or adult patients from 1 to 45 years old with ALL who experience hypersensitivity reactions (clinical allergic reaction or silent inactivation) to PEG-ASNase.

All patients will receive the NOPHO ALL 2008 or ALLTogether pilot protocol chemotherapy regimen, which consists of an induction treatment, consolidation, delayed intensification phase, maintenance phases, a CNS prophylaxis and interim maintenance for a total of 30 months' treatment duration. Once a patient presents with hypersensitivity to PEG- ASNase, eryaspase will be given as a replacement therapy for remaining scheduled PEG-ASNase administrations, Figure 1, **Figure 2**.

Eryaspase will be administered every two weeks for a maximum of four doses, and then administered every 6 weeks for three doses to the end of planned treatment according to the NOPHO ALL 2008 protocol. For patients in the ALLTogether pilot protocol, eryaspase will be administered every 2 weeks for a maximum of 7 doses. The duration of treatment with eryaspase will be dictated by the remaining number of intended courses following the occurrence of hypersensitivity to PEG-ASNase, and therefore it may range between 1-7 doses of eryaspase.

[figure not shown]
Assessments include overall safety profile of eryaspase, PK/PD parameters of eryaspase, immunogenicity of eryaspase, during successive courses of treatment with eryaspase.

Primary trial assessments for each patient will continue for one month following the end of the planned eryaspase treatment phases (approximately 6 months in case of 7 doses). Each patient will receive treatment in about 22 months after last administration of eryaspase according to the NOPHO ALL 2008 or ALLTogether pilot protocol. After cessation of therapy, patients will be followed for recurrence of disease or the development of late effects. The follow-up after cessation of therapy should be done according to guidelines on each country and site, but no assessments of those will be included for this study.

Sponsor:	NOPHO – Nordic Society of Pediatric Hematology & Oncology		
Protocol:	NOR-GRASPALL 2016		
Document Version No.:	2.0	Document Date:	14-May-2021

[figure not shown]
Figure 1 Study Diagram – Patients Treated According to NOPHO ALL 2008

Sponsor:	NOPHO – Nordic Society of Pediatric Hematology & Oncology		
Protocol:	NOR-GRASPALL 2016		
Document Version No.:	2.0	Document Date:	14-May-2021

Figure 2 Study Diagram – Patients Treated According to NOPHO ALLTogether

Once Eryaspase is initiated, PEG-Asparaginase regimen should be replaced by scheduled Eryaspase during all remaining chemotherapy course

 Peg-Asparaginase
 Eryaspase dose: 150 U/kg IV infusions will be administered every 2 weeks for maximum 3-7 doses up to the end of planned chemotherapy according to protocol and risk group

*According to ALLTOGETHER protocol: VLR: 4 doses IR low: 5 doses IR high: 8 doses

Sponsor:	NOPHO – Nordic Society of Pediatric Hematology & Oncology		
Protocol:	NOR-GRASPALL 2016		
Document Version No.:	2.0	Document Date:	14-May-2021

3.2. Randomization Methodology

Not Applicable

3.3. Stopping Rules and Unblinding

Not Applicable

Sponsor:	NOPHO – Nordic Society of Pediatric Hematology & Oncology		
Protocol:	NOR-GRASPALL 2016		
Document Version No.:	2.0	Document Date:	14-May-2021

3.4. Study Procedures

The schedule of assessments, as outlined in the study protocol, is provided in Error! Reference source not found..

Table 1 Schedule of Assessments

Time/day	Screening	Week 1			Week 2												
		≥ 5 days (Course 1)	Baseline ^a (Day 1)	1	2	3	4	5	6	7	8	9	10	11	12	13	14
Assessment																	
Eligibility check	X ^b																
Signed written informed Consent	X ^b																
Baseline data (Demographics, medical history, ALL disease history)	X ^b																
Physical examination and vital signs incl. Karnofsky/Lansky Score	X			X													
ALL clinical assessment	X																
Pregnancy test ^c	X																
Weight	X															X	
Ordering/Quality check																	
Blood phenotyping		X ^{c,d}															
Prescription/ordering		X ^e															
Irregular Antibody Screening Test		X ^f (< 72 hours)															
Serologic crossmatch ^g		X															

Sponsor:	NOPHO – Nordic Society of Pediatric Hematology & Oncology		
Protocol:	NOR-GRASPALL 2016		
Document Version No.:	2.0	Document Date:	14-May-2021

Study Calendar, 6-Weeks Courses

Sponsor:	NOPHO – Nordic Society of Pediatric Hematology & Oncology		
Protocol:	NOR-GRASPALL 2016		
Document Version No.:	2.0	Document Date:	14-May-2021

CRS-BS-TP-000005 V 1.0

CRS-BS-TP-000005 V 1.0

Page 20 of 46

Client / Cyrel Confidential: This is a controlled document and shall not be changed, saved, copied or reproduced by any unauthorized person.

Sponsor:	NOPHO – Nordic Society of Pediatric Hematology & Oncology		
Protocol:	NOR-GRASP ALL 2016		
Document Version No.:	2.0	Document Date:	14-May-2021

- b. Complete section 3 and 4 in the CRF and please send it to: [contact]
- c. Complete “Blood group form” (appendix 3 in the IMP manual) and attach lab results → send to Erytech pharma: [contact] (or [[contact]]([contact]))
- d. Only before the first administration → Send the documents to Erytech Pharma at the latest 5 working days prior to each eryaspase administration.
- e. Complete the “prescription form” (appendix 4 in the IMP manual) → Send the documents to Erytech Pharma in case of positive results, contact Erytech pharma immediately → blood sample must be shipped to Erytech [contact] (or [[contact]]([contact]))
- f. 72-48 hours before administration → send lab results for Erytech Pharma. In case of positive results, contact Erytech pharma immediately → blood sample must be shipped to Erytech pharma/French blood bank for serologic cross match → follow guidelines in IMP manual.
- g. A serologic crossmatch test between the patient's blood and the IMP is required to ensure IMP administration under safe conditions. This test can be done at the local lab or blood bank using one of the removable segment-tubes attached to the IMP bag. Complete Safety and administration form (appendix 5 in IMP manual). Erytech will now be testing blood in case of incompatibility with IMP, regardless of IAST positivity.
- h. Blood sampling will be modified by local conditions and activities planned in the NOPHO ALL 2008 protocol. Aimed time slot is marked in this study calendar (1-7) and is described in the research protocol in section 8.4 and below here (#1-7). Date and time of blood sampling must be registered in the CRF. PK sample times for each course: 15 min (\pm 5 min) before eryaspase administration; End of infusion (0-10 min); 24 hours post-infusion (\pm 1 day); 3 days (\pm 1 day); 6 days (\pm 1 day); 24 hours (\pm 2 hrs); 3 days (\pm 2 days) post-infusion; 10 days (\pm 2 days) post-infusion; 14 days (\pm 2 days) post-infusion; 21 days (\pm 2 days)
- i. Every effort will be made to collect these samples.
- j. Samples must be sent to: *Pediatric research Laboratory, Aarhus University Hospital, [name], [name], Denmark. Att. [name]. Please notify by email before the shipment: [contact]*
- k. When planned in NOPHO ALL 2008 protocol.
- l. Must be send on dry ice to: *Pediatric research Laboratory, Aarhus University Hospital, [name], [name], Denmark. Att. [name]. Please notify by email before the shipment: [contact]*. Samples can be sent at the end of study period
- m. In connection with measurements of maintenance metabolites. Lab results must be attached with the CRF. Send the samples to Bonkolah, Copenhagen according to the NOPHO protocol.
- n. Blood samples includes: Hematological parameters (Hemoglobin, thrombocytes, Differentiated White Blood Cell Count) and liver parameters (bilirubin, alanine aminotransferase (ALAT), Lactate dehydrogenase (LDH)).
- o. Serum human chorionic gonadotropin pregnancy test at screening in women of child-bearing potential and sexually active women that are of child-bearing potential is required.
- p. Biological safety parameters are recommended and include: Hematological parameters (Hemoglobin, thrombocytes, Differentiated White Blood Cell Count) and liver parameters (bilirubin, alanine aminotransferase (ALAT), Lactate dehydrogenase (LDH), amylase, lipase, triglycerides and cholesterol, urinary glucose and coagulation parameters (partial thromboplastin time (PTT), prothrombin time (PT), antithrombin III and fibrinogen))
- q. Be attentive to events from last course at baseline of next course. Please complete the CRF and send it after each course ([contact]). Guidelines to registration is found in the CRF.
- r. Registration of other cytostatic treatment including maintenance therapy (according to the NOPHO ALL 2008 protocol) in the CRF.
- s. Blood samples at day 14 coincide with baseline of next course. If applicable examinations are not needed to be repeated at both time points.
- t. Additional blood counts for biological safety can be performed due to clinical conditions and as standard of care.

Sponsor:	NOPHO – Nordic Society of Pediatric Hematology & Oncology		
Protocol:	NOR-GRASPALL 2016		
Document Version No.:	2.0	Document Date:	14-May-2021

4. GENERAL STATISTICAL CONSIDERATIONS AND DATA HANDLING

4.1. Sample Size Justification

The trial is powered to test the hypothesis that 70% of patients meet the >100 U/L threshold compared to the null hypothesis that this threshold is achieved in 50% of patients. The null and alternative hypotheses stated here align with those outlined in previous FDA approvals, such as CDER Application (125359Orig1s000) for Erwinaze in the treatment of ALL. Based on a one-sided significance level of 2.5%, a total of 49 patients will provide 80% power for this comparison in an exact binomial test. A total of 55 patients will be recruited to allow for a ~10% dropout rate for an analysis based on evaluable patients.

Originally, the study was planned for 30 patients. An interim analysis was conducted after first 18 patients enrolled into the study, and study continued to enroll all 35 patients. The protocol was amended in August 2019 to increase the sample size up to 55 patients. The sample size increase was prompted by:

1. Continuous Erwinaze shortage and the need to complete the intended courses of asparaginase therapy
2. Encouraging safety and efficacy profile based on the informal interim analysis in the first 18 patients
3. Note that the sample size increase was not based on any evaluation of the primary endpoint from the study data collected up to that point

The primary population for analysis will be the Evaluable Patient population defined as all patients recruited into the study who provide data on whole blood ASNase activity on Day 14 (+/- 2 days) following the first administration of eryaspase.

A formal statistical hypothesis test will be performed on the primary endpoint. A single sample binomial test will be used to test the null hypothesis at the 2.5% one-sided significance level. The key secondary endpoint with the threshold of 100 U/L following the fourth infusion will be evaluated in the same way. Multiplicity will be controlled across the primary and key secondary endpoint through a pre-specified hierarchy with the primary endpoint in position 1 and the key secondary endpoint in position 2.

Descriptive statistics will be presented. For binary endpoints, 95% confidence intervals for the observed proportions will be calculated using Wilson Score method.

Sponsor:	NOPHO – Nordic Society of Pediatric Hematology & Oncology		
Protocol:	NOR-GRASPALL 2016		
Document Version No.:	2.0	Document Date:	14-May-2021

4.2. General Methods

The primary statistical analyses will be performed using cleaned eCRF data.

All output will be incorporated into Microsoft Excel or Word files, sorted and labeled according to the International Conference on Harmonisation (ICH) recommendations, and formatted to the appropriate page size(s).

Tabulations will be produced for appropriate demographic, baseline, efficacy, pharmacokinetic and safety parameters. For categorical variables, summary tabulations of the number and percentage within each category (with a category for missing data) of the parameter will be presented. For continuous variables, the mean, median, standard deviation, minimum and maximum values will be presented. Time to event data will be summarized using Kaplan-Meier Methodology using 25th, 50th (median), and 75th percentiles with associated 2-sided 95% confidence intervals, as well as percent of censored observations.

The following general data handling conventions, will be used in derivation of variables used in data summaries and analysis:

Term	Definition/Rule
Date of diagnosis of ALL	Date of initial ALL diagnosis
Start date of exposure period	Start date of eryaspase treatment
End date of exposure period	The end date of treatment exposure is defined as follows, depending the one occurs first: 
 • 30 days after the last treatment administration • relapse • Death
Study Day	(date of assessment) - (date of first study drug dose) + 1
Months	Study days divided by 30.4375 days
Years	Study days divided by 365.25 days
Baseline	The latest measurement performed during screening and prior to the first dose of study drug. If the baseline value is missing, then the latest non-missing value generated prior to first dose of study drug will be used as the baseline value
Time to Event (i.e., RFS or EFS)	(date of the event) - (randomization date) + 1
Age	(date of informed consent - date of birth)/365.25 rounded down

Sponsor:	NOPHO – Nordic Society of Pediatric Hematology & Oncology		
Protocol:	NOR-GRASPALL 2016		
Document Version No.:	2.0	Document Date:	14-May-2021

Term	Definition/Rule
Date of diagnosis of ALL	Date of initial ALL diagnosis
Total duration of treatment	(date of last dose) – (date of first dose) + 1

4.3. Computing Environment

All statistical analyses will be performed using Statistical Analysis Systems (SAS®) release 9.2 or higher, or RStudio Version 1.2.5001, unless indicated otherwise.

Medical history and AEs will be coded using the Medical Dictionary for Regulatory Activities (MedDRA) version 21.0. The intensity of AEs will be graded according to the NCI-CTCAE (version 5.0). Concomitant medications will be coded using World Health Organization (WHO) Drug version B3 June 2018.

4.4. Methods of Pooling Data

Not applicable to the present study.

4.5. Pharmacokinetic, pharmacodynamic, efficacy and safety variables

4.5.1. Pharmacokinetic, Pharmacodynamic, and Immunogenicity Variables

Eryaspase PK will be evaluated using robust sampling. Blood samples for determination of whole blood asparaginase pharmacokinetics were to be collected as outlined in **Error! Reference source not found..**

Whole blood samples will be analyzed using an enzymatic assay in which the L-AHA is hydrolyzed leading to the production of aspartic acid and hydroxylamine. Following centrifugation, the supernatant containing hydroxylamine is diluted with 8-hydroxiquinoline. The formation of indooxine after oxidation of hydroxylamine and 8-hydroxiquinoline is proportional to asparaginase activity and can be detected by absorbance reading.

Pharmacokinetic parameters to be determined include: maximum plasma concentration (Cmax), time to maximum plasma concentration (Tmax), trough concentration (Ctrough), elimination rate constant (λ_z), terminal phase half-life (t_{1/2}), area under the concentration versus time curve (AUC), mean residence time (MRT), clearance (CL), and volume of distribution at steady state (V_{ss}).

Sponsor:	NOPHO – Nordic Society of Pediatric Hematology & Oncology		
Protocol:	NOR-GRASPALL 2016		
Document Version No.:	2.0	Document Date:	14-May-2021

The pharmacodynamic effect of eryaspase on amino acid levels will be evaluated in patients, where CSF samples are collected. Reverse phase high performance liquid chromatography will be used to measure amino acids.

Immunogenicity variables include the presence of screening, confirmatory and neutralizing anti-asparaginase antibodies over time.

4.5.2. Safety Variables

Safety assessments performed during the study included clinical laboratory evaluations including hematology, serum chemistry, and monitoring of adverse events.

4.6. Analysis populations

The following patient populations will be evaluated and used for presentation and analysis of the data:

4.6.1. Evaluable Patients (EP) Population

This is the primary population for the analysis of the primary and key secondary endpoint(s), defined as all patients recruited into the study who provide data on asparaginase level on Day 14 (+/- 2 days) following the first administration of eryaspase.

The evaluation of the secondary endpoints will also be based on this population but without any imputation for missing data.

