4.6.2. Per Protocol (PP) Population

All patients in the Evaluable Patients Population without major protocol deviations.

Sensitivity analyses for the primary and key secondary endpoint will be undertaken for the PP population.

Below are the examples of major protocol violations that will exclude patients from the PP population:

- No written informed consent
- No evidence of hypersensitivity reactions/silent inactivation to PEG-ASNase.
- Investigational Medicinal Product (IMP) non-safety related issues that led to delaying or skipping eryaspase dose; these include, but not limited to: RBC cross match incompatibility, IMP delivery issues, other logistical issues.

Sponsor:	NOPHO – Nordic Society of Pediatric Hematology & Oncology		
Protocol:	NOR-GRASPALL 2016		
Document Version No.:	2.0	Document Date:	14-May-2021

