4.6.3. Safety Population

The Safety Population will consist of all patients enrolled in the study who received at least one dose of eryaspase. Safety data will be analyzed using actual dose initially received.

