4.6.4. Pharmacokinetic Population

The Pharmacokinetic Population will consist of all patients with an evaluable maximum concentration (Cmax), area under the curve from time 0 to the last measurable concentration (AUC(0-t)), and Ctrough for whole blood ASNase following the first infusion. Analyses of PK data will not use any missing data imputation and will be based solely on observed data.

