4.11.1. Asparaginase Activity and Amino Acids

Missing asparaginase activity data will not be replaced or imputed.

Similar rules will be followed for calculating ASN and GLN levels.

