6.2. Analysis of Key Pharmacokinetic Secondary Endpoints

6.2.1. Pharmacokinetic Parameter Calculations

Pharmacokinetic parameter analyses will be conducted using the Pharmacokinetic Population. The pharmacokinetic parameters to be determined are summarized below, Table 3:

Table 3 **Pharmacokinetic Parameters for Analysis**

Parameter	Description
Cmax	Maximum observed concentration after each administration
tmax	Time corresponding to occurrence of Cmax
Ctrough	Observed concentration at the end of each dosing interval
t1/2	Apparent terminal elimination half-life
AUC(0-t)	AUC from time zero to the last quantifiable concentration
AUC(0-inf)	AUC from time zero extrapolated to infinity following first administration
%AUCex	Percentage of AUC(0-inf) obtained by extrapolation following first administration
MRT	Mean Residence Time
CL	Clearance following first administration
Vss	Volume of distribution following first administration

Sponsor:	NOPHO – Nordic Society of Pediatric Hematology & Oncology		
Protocol:	NOR-GRASPALL 2016		
Document Version No.:	2.0	Document Date:	14-May-2021

PK parameters will be calculated by non-compartmental analysis (NCA) methods from the whole blood concentration-time data using Phoenix WinNonLin version 8.0 and following these guidelines:

- Actual sampling times relative to dosing rather than nominal times will be used in the calculation of all derived PK parameters.
- There will be no imputation of missing concentration data.
- Any subjects with missing concentration data will be included in the PK analysis set provided that at least Cmax and AUC(0-t) can be reliably calculated
- All below the limit of quantification (BLQ) values pre-dose will be substituted by zeros; thereafter, BLQ values between evaluable concentrations will be set to missing
- PK parameters will be estimated according to the following:
 - Cmax and Ctrough will be obtained directly from the concentration-time data.
 - tmax is the time at which Cmax is observed.
 - The terminal phase rate constant (λz) will be estimated by linear regression after log-transformation of the concentrations:
 - Only those data points that are judged to describe the terminal log-linear decline will be used in the regression.
 - A minimum number of three data points in the terminal phase will be used in calculating λz with the line of regression starting at any post-Cmax data point

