6.2.2. Pharmacokinetic Tables, Figures and Listings

Pharmacokinetic concentration data will be listed by subject including actual sampling times relative to dosing. Whole blood ASNase concentrations will be summarized by dosing course. The following descriptive statistics will be presented for concentrations obtained at each nominal time point: n, arithmetic mean, SD, coefficient of variation (CV%), median, minimum and maximum values.

Pharmacokinetic parameters will be listed by subject and summarized by course following the first and fourth infusion of the 2-week regimen. Descriptive statistics for calculated PK parameters will include n, arithmetic mean, SD, CV%, geometric mean, median, minimum, and maximum values. For t_{max}, only median, minimum, and maximum values will be presented.

Individual whole blood concentration versus actual times will be plotted by course in linear and semi-logarithmic scale. Mean and median concentrations versus nominal times will also be presented in linear and semi-logarithmic scale by course.

All concentrations below the limit of quantification (BLQ) or missing data will be labeled as such in the concentration data listings. Missing samples will be reported as no sample ("NS") and excluded from analysis. Values that are BLQ will be substituted with zero for the calculation of descriptive statistics of concentration by time point and will be displayed as "not calculable" or NC for the calculation of statistical summaries.

For graphs of arithmetic means and medians, all BLQ mean concentrations will be substituted by zeros. Any arithmetic mean or median that is BLQ will be excluded from log/linear presentation. Any BLQ values prior to the last quantifiable concentration will be plotted as zero for individual linear/linear graphs and excluded from log/linear graphs. All BLQ values after the last quantifiable concentration will be excluded from individual linear/linear and log/linear graphs.

All analyses will be based on the Pharmacokinetic Population.

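### The infusion-4 test can lose patients stopped for allergy or absent activity, and no planned analysis of either tested percentage covers all treated patients

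*SAP*

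**What the plan says.** **Population for both tests.** SAP 4.6.1 makes EP the primary population for the primary and the key secondary endpoint, and fixes entry at the first infusion: "all patients recruited into the study who provide data on asparaginase level on Day 14 (+/- 2 days) following the first administration of eryaspase". SAP 4.1 evaluates the key secondary endpoint like the primary, second in a fixed hierarchy.

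**Missing values.** SAP 4.11.1: "Missing asparaginase activity data will not be replaced or imputed". SAP 4.6.1 adds: "The evaluation of the secondary endpoints will also be based on this population but without any imputation for missing data". No section says how an EP patient without an infusion-4 value is counted.

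**Sensitivity analysis.** The one population named for it is Per Protocol (SAP 4.6.2): "All patients in the Evaluable Patients Population without major protocol deviations".

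**All treated patients.** The Safety Population (SAP 4.6.3) is "all patients enrolled in the study who received at least one dose of eryaspase", but neither tested percentage is assigned to it.

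**A stray population statement.** SAP 6.2 is headed "Analysis of Key Pharmacokinetic Secondary Endpoints", and 6.2.2 ends: "All analyses will be based on the Pharmacokinetic Population". That population requires first-infusion Cmax, AUC(0-t) and Ctrough (SAP 4.6.4). SAP 6.2.3 goes back to the evaluable population.

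**Stopping and schedule.** Protocol 7.6 discontinues eryaspase for, among other reasons, clinical allergy of any grade and absence of asparaginase activity. The number of eryaspase doses ranges from 1 to 7 (Protocol 5.1; SAP 3.1).

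**The concern.** The trial asks whether patients hypersensitive to PEG-asparaginase can be kept on an active asparaginase. For that question, a patient taken off eryaspase because of a reaction to it, or because activity has gone, is a failure. The infusion-4 percentage is formally tested, yet its population is set one infusion into treatment and needs a value that such a patient cannot supply. One route out of the denominator (no activity) is the opposite of the outcome being counted, so this is selection related to the outcome and not random missingness.

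The planned sensitivity analysis cannot reveal the effect, because Per Protocol only removes further patients from EP. If the rule for these patients is settled after the data are known, the choice of denominator could decide whether the key secondary test is reported as met.

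**Working it through.** **Inputs.** Null 50%, alternative 70%, one-sided 2.5%, exact binomial, 49 evaluable of 55 recruited (SAP 4.1). Stopping reasons: Protocol 7.6. The number planned for a fourth 2-week infusion and the number stopped before it are not in the documents, so the values below are assumptions.

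**Step 1: reproduce the plan.** The p-value for r responders of n is the sum of C(n,i) × 0.5^n for i = r to n. At n = 49 the smallest passing count is 32 (p = 0.0222; 31/49 gives 0.0427). Power at 70% is P(X ≥ 32 | 49, 0.7) = 0.810. Allowing for 10% dropout, 49/0.9 = 54.4, rounded up to 55. The SAP's figures hold; the issue is the denominator.

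**Step 2: trace a patient.** A patient has a Day 14 value after infusion 1 and enters EP. Before infusion 4 the patient is stopped for allergy or no activity. There is no infusion-4 value and nothing is imputed. The patient leaves the infusion-4 percentage unless the SAP says otherwise, and it does not.

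**Step 3: illustrate at the boundary.** Assume 20 planned and 2 stopped.

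- Complete case, 14/18: (3060 + 816 + 153 + 18 + 1)/2^18 = 4048/262144 = 0.0154, passes.
- Stops counted as non-response, 14/20: 60460/1048576 = 0.0577, does not pass.
- One more responder, 15/20: 21700/1048576 = 0.0207, passes.

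Other assumed cases, each at the smallest passing complete-case count:

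| Planned | Stopped | Complete case | Stops as non-response |
|---|---|---|---|
| 30 | 2 | 20/28, p=0.018 | 20/30, p=0.049 |
| 40 | 3 | 25/37, p=0.024 | 25/40, p=0.077 |
| 20 | 1 | 15/19, p=0.010 | 15/20, p=0.021 (no reversal) |

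**Step 4: how large could n be?** NOPHO ALL 2008 gives five PEG-asparaginase doses at 2-week intervals, and 85% of the Nordic children with allergy reacted after dose 2 or 3 (Protocol 1.0). That leaves 5 − 2 = 3 or 5 − 3 = 2 of the 2-week doses, so at most 15% of that group would reach a fourth (more if the reacting dose is given again as eryaspase). This does not cover ALLTogether patients, adults or silent inactivation. It shows only that n may be well below 49 and that the SAP gives no expected value.

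**Step 5: primary endpoint, worst case.** Assume all 55 are treated and 6 have no Day 14 value. Then 32/49 (p = 0.022) becomes 32/55 (p = 0.140) if all 6 count as non-response.

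**The case against.** **The endpoint presupposes a fourth infusion.** Activity 14 days after infusion 4 is a trough measure, and counting patients who never received that infusion answers a treatment-strategy question instead. This stands. A reader might infer that the planned test exceeds its 2.5% level. With 20 planned, 2 stopped and a true all-planned rate of 50%, the rate among those left is 10/18 = 55.6% and the complete-case test rejects 4.5% of the time. But for the question the EP test asks (50% among those with a value), the rejection rate is 1.5%. The documents do not support a claim of inflation.

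**The population is not really in dispute.** A reader might infer that the SAP contradicts itself. SAP 4.1, 4.6.1, 4.6.2 and 6.2.3 all point to EP for the key secondary endpoint. The sentence in 6.2.2 closes a subsection on PK tables and most likely refers to concentrations and parameters. The no-imputation sentence in 4.6.1 can also be read as covering the key secondary endpoint. These are loose wordings to tidy, not a conflict that changes the analysis.

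**The primary endpoint is little affected.** A reader might infer the same bias there. A sampled patient with low activity stays in EP as a failure, Day 14 is a scheduled sample (Protocol 8.4.1), and patients who stop are followed for at least a month (Protocol 8.1). SAP 4.1 also openly plans an analysis of evaluable patients. Bias in the primary percentage is possible but speculative.

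**Failures are visible elsewhere.** Hypersensitivity incidence (SAP 2.4.4), discontinuation by reason (SAP 5.1) and completion of planned doses (SAP 7) are reported. A reader could build a bound by hand, but it would not be pre-specified, and the tested percentage would still omit these patients.

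**The reversals sit at the rejection boundary.** True: one more responder removes the first two, two more remove the third (27/40, p=0.019), and the infusion-4 test is formal only if the primary succeeds.

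**Conclusion.** The concern holds for the key secondary test. On the complete-case reading, which the SAP neither states nor excludes, the infusion-4 percentage can lose patients because eryaspase failed in them. No pre-specified analysis would show it, and neither tested percentage is analysed in all treated patients.

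The size cannot be computed. Protocol 2.1.2 reports an 11.5% allergic-reaction rate in previously allergic patients in the pivotal trial, but no withdrawals for hypersensitivity there; the present protocol stops for allergy of any grade. Neither figure gives a stop rate before infusion 4. The counts in the working are assumptions chosen at the boundary. They show that two or three stopped patients can matter, not that they will. The point should be fixed, but it does not invalidate the EP tests.

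**What to change.** Keep both EP tests as planned.

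1. In SAP 4.6.1 and 6.2, state that the infusion-4 test uses EP patients with a Day 14 value after the fourth 2-week infusion, and report that n.
2. Add a pre-specified sensitivity analysis of the infusion-4 percentage in treated patients whose remaining 2-week schedule included a fourth infusion. Count those permanently stopped for an eryaspase-related reason (allergy, no activity, toxicity) before Day 14 of infusion 4 as non-responders. Patients never scheduled for a fourth 2-week infusion are left out, not failed. Where the ALLTogether risk group was not yet assigned at stopping, show the result with and without the patient.
3. As a companion, report the primary percentage in the Safety Population with a missing Day 14 value counted as non-response, labelled as a worst-case bound.
4. Say that the closing sentence of 6.2.2 refers to PK concentrations and parameters, and align the imputation wording of 4.6.1 with 4.11.1.

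**Cost.** SAP wording and one or two tables. Reasons for stopping are already to be tabulated (SAP 5.1); whether a fourth 2-week infusion was planned must be derivable for each patient. The added percentages will be equal or lower, with less power:

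- With 20 planned, 2 stopped and 70% response among the 18 left, the sensitivity analysis needs 15 responders: P(X ≥ 15 | 18, 0.7) = 16%, against P(X ≥ 14 | 18, 0.7) = 33% for the complete-case test.
- For the primary bound, with 6 of 55 counted as non-response, 36 responders are needed: P(X ≥ 36 | 49, 0.7) = 36%, against 81% for the EP test.

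For that reason they should be sensitivity analyses, not replacements.
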